## 1. Protocol Summary

### 1.1. Synopsis

**Protocol Title:** EEG-based depth of anesthesia monitoring – effects on wake-up times and cognition.

**Short Title:**

**Rationale:**

Depth of anesthesia-monitoring (DoA-mon) based on EEG changes demands knowledge about the effects of the different anesthetic medications on EEG waveforms. We want to investigate the use of the raw-EEG waveform in addition to indexes (BIS) and EEG spectrogram analyses for depth of anesthesia monitoring. We hypothesize that with the use of this monitoring, we will be able to better individualize the dosage of anesthetic drugs, and that this will reduce the total consumption of anesthetic medication, thus reducing time to wake-up after surgery. Some studies have indicated that too deep anesthesia, confirmed by "burst-suppression" or isoelectric-EEG, is associated with increased postoperative cognitive dysfunction (POCD). We will therefore assess the patients with the Cambridge Neuropsychological Test Automated Battery (CANTAB) cognitive function assessment tool.

### Objectives and Endpoints

Objectives	Endpoints
Primary	

 
Use of DoA-mon reduces anesthetic dosage and wake-up times
 
	
 
Total amount of propofol (mg/kg/hr) administered
 
Time to wake-up after halt of anesthetic administration
 

Secondary	

 
Use of DoA-mon reduces POCD
 
	
 
Cognitive functioning
 

### Overall Design

**Disclosure Statement:** This is an interventional study. The study has two arms, and is single blinded for the participant, and assessment masked for the investigator. It is blinded for the post-operative care providers.

**Number of Participants:100**

Approximately 200 patients will be screened to achieve enrolled to study intervention and 100 evaluable participants for an estimated total of 50 evaluable participants per intervention group.

**Intervention Groups and Duration:**

Perioperatively guiding depth of anesthesia by EEG-based monitoring, assessed preoperatively 1 day before surgery, and at 3 hours, and at 24 hours after surgery.

**Data Monitoring :**

Yes, by clinical trial units monitor [name].

## 1.2. Schedule of Activities (SoA)

Procedure	Screening (up to 14 days before Day 1)	Intervention Period Days/Hours				Comments
		-1	1 directly prior to surgery	1 / 3 hrs after surgery	2 / 24 hrs after surgery	
Informed consent	X	X				
Inclusion and exclusion criteria	X					
physical examination	X					Standard preoperative/anesthetic assessment
Height and weight		X				
Medical history	X					
Vital signs		X	X	X		
Pain and sedation level assessment		X	X	X	X	VAS scale/RASS sedation score
Randomization			X			
Study intervention			X			
CANTAB cognitive assessment	X			X	X	
AE review				X	X	

## 2. Introduction

Depth of anesthesia-monitoring based on EEG changes demands knowledge concerning the effects of the different anesthetic medications on EEG waveforms. We want to investigate the use of the raw-EEG waveform in addition to indices (BIS) and EEG spectrogram analyses for depth of anesthesia monitoring. We hypothesize that with the use of this monitoring, we will be able to better individualize the dosage of anesthetic drugs, and that this will reduce the total consumption of anesthetic medication, thus reducing time to wake-up after surgery. Some studies have indicated that too deep anesthesia, confirmed by "burst-suppression" or isoelectric-EEG, is associated with increased postoperative cognitive dysfunction (POCD). We will therefore assess the patients with the Cambridge Neuropsychological Test Automated Battery (CANTAB) cognitive function assessment tool.

### 2.1. Study Rationale

To investigate options to individualize anesthetic dosage based on the EEG-responses to hypnotic drugs during general anesthesia. This to potentially reduce total amount of anesthetic drugs administered, and henceforth possibly reduce postoperative cognitive dysfunction after surgery and anesthesia.

### 2.2. Background

It has been over 80 years since Gibbs et al (1) showed how the electroencephalogram (EEG) systematically changed in concurrence with increasing doses of hypnotic drugs such as pentobarbital and Ether. The study concluded that "Electroencephalography may therefore be of value in controlling depth of anesthesia and sedation". In spite of a solid documentation of the systematic connection between dosing of anesthetic drugs, EEG-patterns and level of sedation/anesthesia (2-8), EEG-based DoA has not become a part of standard of care in anesthetic management. There is abundant evidence of how different anesthetic drugs leads to characteristic fluctuations in human brain electrical activity, relating to depth of anesthesia, anesthetic drug of choice, and age (7,8,9-15). These anesthetic induced fluctuations are readily visible as changes in the patients EEG.

Anesthetic drugs are usually administered in pharmacological models based on a population taking into account their age, weight and height. However, there is a significant difference in how patients respond to these models. In adults there is evidence that the doses needed to achieve consciousness varies with a factor of 2 above and below suggested doses (20). In underdosing of anesthetics there is a risk of perioperative awareness (21,22). On the other hand there is also evidence that overdosing of anesthetics has harmful effects; children receiving more than 4% Sevoflurane can demonstrate epileptiform activity (23,24), and adults overdosing into "burst suppression" during anesthesia has a higher risk of postoperative delirium (POD) and increased occurrence of postoperative cognitive dysfunction (POCD) (25,26).

Bispectral Index (BIS) is an algorithm developed by Aspect Medical Systems in 1994, which is based on weighted sums of EEG subparameters to present an index from 0 to 100 for depth of anesthesia, where 100 is wide awake, and 0 is an isoelectric EEG. The BIS target for a deep

enough anesthesia is set to be between 40 and 60. The BIS number is often in concurrence with other clinical observations related to anesthetic depth, however there is also an experience of divergence. BIS and other EEG-based indices are programmed from adult cohorts, and cannot be directly trusted in children, or the elderly (29,30). There is also an incapability in these preprogrammed indices (BIS and other) to integrate how specific anesthetic drugs affect the EEG, and thenceforth the BIS value. An example of this is how the drug Ketamine induces a specific gamma-frequency in the EEG, which the BIS-index translates as a lighter anesthesia, even though the drug is administered “on top of” an already deep level of anesthesia.

### **2.3. Benefit/Risk Assessment**

The benefit for the participants in this study is an increased attention from the anesthetic staff, and that the monitoring of levels of anesthesia will be standardized and thorough regardless of which study-group you wind up in. The risk of awareness during surgery is what we always achieve to avoid, and the risk of this is low in both study-arms. We will screen for this after surgery; all patients will be interviewed to assess their experience of the procedure, what they remember and overall satisfaction with our treatment.

Both arms of the study represents ways of delivering general anesthesia in surgery today. The incidence of awareness in North America and Europe is 1 to 2 cases/1000 (45-50). A 2019 meta-analysis of randomized trials compared BIS-EEG guidance of anesthetic depth to reduce the risk of awareness from 9 to 3 pr 1000 (51). So there is a small possibility that the intervention reduces the risk for awareness for the participants in this study.

### 3. Objectives and Endpoints

Objectives	Endpoints
Primary	

• Use of DoA-mon reduces anesthetic dosage and wake-up times

	

• Total amount of propofol (mg/kg/hr) administered

• Time to wake-up after stop of anesthetic administration

Secondary	

• Use of DoA-mon reduces POCD

	

• Cognitive functioning

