#### 4.3.1 End of Study Definition

A participant is considered to have completed the study if he/she has completed all phases of the study including the last assessment on day 2 of surgery.

The end of the study is defined as the date of the last visit of the last participant in the study.

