#### **9.4.3. Secondary endpoint(s)**

Time to wake-up; from halt of anesthetic drugs to

- extubation (sec)
- Verbal respons (sec)
- Motoric response (show right index finger)(sec)

Medication usage of remifentanil micg/kg/min

Medication usage of inotropes (phenylephrine, norepinephrine)

Cognitive function, assessed with 4 trials in the CANTAB IPAD-tool, preoperative function compared with 3hrs after wake-up, and preoperative compared with 24 hrs after wake-up.

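### The secondary objective claims a reduction in POCD, but cognition is tested after surgery only at 3 h and 24 h, and a 3 h difference could simply be faster recovery from anesthesia

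*Protocol*

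**What the plan says.** The objectives tables in Protocol 1.1 and 3 give the secondary objective as "Use of DoA-mon reduces POCD" and pair it with the endpoint "Cognitive functioning". Section 9.4.3 also calls the outcome cognitive function and lists two comparisons: "preoperative function compared with 3hrs after wake-up, and preoperative compared with 24 hrs after wake-up".

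The synopsis (Intervention Groups and Duration) has participants "assessed preoperatively 1 day before surgery, and at 3 hours, and at 24 hours after surgery". The Schedule of Activities (1.2) marks CANTAB once before surgery and then at 3 h and 24 h; its last column is "2 / 24 hrs after surgery". Under 4.3.1 a participant is done on having "completed all phases of the study including the last assessment on day 2 of surgery". No later cognitive test is planned.

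The Rationale in 1.1 expects of the monitoring that "this will reduce the total consumption of anesthetic medication, thus reducing time to wake-up after surgery". Section 9.2 puts the propofol reduction at up to 20%, and 9.1 puts the gain in wake-up at 3 min. The Rationale links POCD to anesthesia that is too deep, shown by burst suppression or an isoelectric EEG. Section 2.1 adds that a lower total dose may itself reduce POCD.

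Pain and sedation ("VAS scale/RASS sedation score") are scheduled at 3 h and 24 h, and also on day -1 and directly before surgery.

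**The concern.** The trial's main hypothesis is that the intervention arm receives less drug and wakes sooner. If that is true, the arms differ in recent drug exposure when cognition is first retested. A better 3 h CANTAB score in the intervention arm then has two possible sources: less drug still acting, or less dysfunction from over-deep anesthesia. The objective names only the second.

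What is at stake is the secondary conclusion. A difference confined to 3 h could be written up as less POCD. Conversely, no difference at 24 h could be written up as no effect on POCD without the limit that nothing after 24 h was examined. The primary analysis and the data collected are not affected.

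**Working it through.** The document gives no figure on this point, so the check is mainly a comparison of sections.

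**1. Claim against measurement.**
- Claim (1.1, 3): POCD is reduced.
- Measured (1.1, 1.2, 9.4.3): CANTAB before surgery, at 3 h and at 24 h. Of the two postoperative tests, none falls after 24 h.
- Name of the outcome in 9.4.3: cognitive function. The analysis section already uses the narrower term; the objective does not.

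**2. What the arms are expected to differ in.**
- Propofol: up to 20% less (9.2).
- Wake-up: 20% of 15 min = 3 min sooner (9.1).

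**3. What each result could mean.**

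| Result | Less residual drug | Less dysfunction | Can the design tell? |
|---|---|---|---|
| Difference at 3 h only | possible | possible | No |
| Difference at 24 h | not supported by the documents | possible | Readable as cognitive function at 24 h |
| No difference at 24 h | – | – | Speaks to the first 24 h only |

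The ambiguity sits in the first row. A statistical analysis plan cannot remove it by creating another assessment.

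**4. Size.** No section quantifies residual drug effect on cognition at either time. The only recovery difference given is 3 min:
- against the 3 h test: 3 / 180 = 1.7% of the interval
- against the 24 h test: 3 / 1440 = 0.2% of the interval

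These fractions describe extra time awake if the clock runs from surgery (taking the stop of anesthetics to coincide with the end of surgery, an assumption). If the clock runs from wake-up, as in 9.4.3, that component is zero. Neither fraction measures a cognitive effect, so the effect at 3 h remains unquantified.

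**5. Time origin.** The synopsis and the Schedule of Activities count 3 h and 24 h from surgery; 9.4.3 counts from wake-up. Counting from wake-up partly aligns the arms for earlier awakening but does not equalise drug exposure.

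**6. Sample size.** The stated 88 is built on wake-up time. With a difference of 3 min, SD 5 min, two-sided 0.05 (sidedness assumed) and 80% power:

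n per arm = 2 × (1.960 + 0.842)² × 5² / 3² = 43.6, so 44, or 88 in total.

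This reproduces the plan (the exact t-test gives 45 per arm, 90 in total). It does not involve cognition, so rewording the objective leaves it unchanged. If all 50 per arm contribute data, a continuous outcome such as the 24 h CANTAB change has 80% power for a difference of about 0.57 SD.

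**The case against.** The other side has a good case on several counts.

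- **Lower dose is the declared route.** Section 2.1 makes reduced exposure the path to less POCD, and in a randomised comparison an effect through that path belongs to the intervention's effect. This stands: a 3 h difference would be a genuine effect on cognition at 3 h. Only its label as POCD is in question.
- **The protocol already holds much of the remedy.** Section 9.4.3 says cognitive function, keeps the two time points apart and counts from wake-up; sedation and pain are scored at both visits. This makes the fix cheap. It does not correct the objective, and the protocol does not link those scores to the cognitive result.
- **Scheduling RASS and VAS proves nothing.** A reader might infer that sedation is expected at 3 h and 24 h because it is scored then. The same assessment is scheduled twice before surgery, so that inference fails.
- **Some detail belongs to the analysis plan.** The rule that turns CANTAB scores into POCD is commonly fixed there, and 9.4 defers technical detail to it. Its absence here is no finding. Objectives and the visit schedule are protocol content.
- **The size is unknown.** One might put a number on the effect by assuming a half-time for residual impairment and proportionality to dose. The documents give neither, and the 20% in 9.2 is an upper bound. This stands, so no size is claimed.

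**Conclusion.** The point holds as a mismatch between objective and endpoint. The objective speaks of POCD; the design measures cognitive function in the first 24 h, and its 3 h result cannot be separated from recovery from anesthesia. This rests on the protocol's own expectation that the intervention lowers propofol exposure and speeds wake-up, and on the plausible but unquantified premise that some drug effect remains at 3 h.

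Three stronger readings are not supported:

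- That faster clearance *would* be reported as less POCD. The text supports only that it *could* be.
- That the 24 h result is affected in the same way. Nothing in the documents points to residual drug effect at 24 h.
- That the trial can say nothing about POCD at all. That would need a rule that POCD cannot be judged at 24 h, and the document contains none.

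The consequence is limited to how a secondary result may be worded. It deserves correction because the correction is nearly free.

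**What to change.** - In 1.1 and 3, reword the secondary objective to: *Use of DoA-mon improves early postoperative cognitive function (CANTAB at 3 h and 24 h)*.
- In 9.4.3, let the 24 h between-arm comparison of change from baseline carry the cognitive conclusion. Interpret the 3 h comparison as early recovery and report it beside the RASS and VAS scores already collected at that visit.
- State that no POCD claim will rest on the 3 h result and that any cognitive conclusion is limited to the first 24 h.
- Reconcile the time origin of the 3 h and 24 h tests between the synopsis and Schedule of Activities (surgery) and 9.4.3 (wake-up).

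The cost is a protocol wording change and a more modest secondary claim. No visits, data or sample size change.

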## 4. Study Design

This is a randomized controlled blinded study, with two groups; intervention and control.

### 4.1. Overall Design

Both groups will receive standard of care in total intravenous anesthesia (TIVA), with monitoring of clinical signs relating to level of anesthesia and to the satisfaction of the surgeon. In the intervention group, the anesthesia providers will guide the dosage of hypnotics based on a BIS-index of 45-60 perioperative, also avoiding burst-suppression (visually detected)/suppression-ratio (SR) of 0, and EEG-frequency alpha (peak alpha) of 10-12 hz.

All patients will have a recording of their perioperative EEG. All patients will be assessed pre and postoperatively using the Cambridge Neuropsychological Automated Test Battery (CANTAB) to assess how they are affected, testing for executive cognitive functioning. The participants use an IPAD to self-assess, so the assessor is blinded.

### 4.2. Scientific Rationale for Study Design

#### 4.2.1. Participant Input into Design

We seek to include patient representation, not in study design, but in the design/text of the participant information leaflet.

#### 4.3.1 End of Study Definition

A participant is considered to have completed the study if he/she has completed all phases of the study including the last assessment on day 2 of surgery.

The end of the study is defined as the date of the last visit of the last participant in the study.

## 5. Study Population

Patients coming to Oslo University hospital Rikshospitalet, for planned elective spinal surgery.

Prospective approval of protocol deviations to recruitment and enrollment criteria, also known as protocol waivers or exemptions, is not permitted.

### 5.1. Inclusion Criteria

Participants are eligible to be included in the study only if all of the following criteria apply:

#### Age

1. Participant must be 18 to 65 years of age inclusive, at the time of signing the informed consent.

#### Sex

2. Male and/or female

#### Informed Consent

3. Capable of giving signed informed consent as described in Appendix 1 which includes compliance with the requirements and restrictions listed in the informed consent form (ICF) and in this protocol

### 5.2. Exclusion Criteria

Participants are excluded from the study if any of the following criteria apply:

#### Medical Conditions

4. Psychiatric disorders
5. Pregnancy
6. Breast feeding
7. Using antiepileptic drugs.
8. Central neurological disease
9. Unable to complete baseline CANTAB-test.

## 6. Study Intervention

Study intervention is defined as any investigational intervention(s), marketed product(s), placebo, or medical device(s) intended to be administered to a study participant according to the study protocol.

### 6.1. Study Intervention(s) Administered

EEG-based DoA-mon, Bilateral BIS from Medtronic, to help guide dosage of anesthetic medication perioperatively.

#### 6.1.1. Medical Devices

1. The manufactured medical device provided for use in this study is the Bilateral BIS by Medtronic. Electrodes are purchased by the hospital, and the medical device company is not a part of this study.

### 6.2. Measures to Minimize Bias: Randomization and Blinding

Included patients randomized blindly	On the day of surgery, the participants are randomized by an outside party to intervention or control group. The patient is blinded to allocated group. All patients are connected to EEG-BIS before sleep, and EEG-device is covered up (for control-group) after they are asleep. Cover is removed before wake-up. Anesthesia providers are masked from assessing outcome. Investigator is masked from assessing cognitive function through patient “self-assessing” using IPAD software.
--------------------------------------	---

## 7. Discontinuation of Study Intervention and Participant Discontinuation/Withdrawal

### 7.1. Discontinuation of Study Intervention

In rare instances, it may be necessary for a participant to permanently discontinue (definitive discontinuation) study intervention. If study intervention is definitively discontinued, the participant will remain in the study to be evaluated.

### 7.2. Participant Discontinuation/Withdrawal from the Study

- A participant may withdraw from the study at any time at his/her own request, or may be withdrawn at any time at the discretion of the investigator for safety, behavioral, compliance, or administrative reasons. This is expected to be uncommon.
- If the participant withdraws consent for disclosure of future information, the sponsor may retain and continue to use any data collected before such a withdrawal of consent.
- If a participant withdraws from the study, he/she may request destruction of any samples taken and not tested, and the investigator must document this in the site study records.

### 7.3. Lost to Follow up

A participant will be considered lost to follow-up if he or she is discharged prior to 24 postop assessment, or unable to be approached for assessment at local hospital due to transfer from Oslo University Hospital.

The following actions must be taken if a participant fails to return to the clinic for a required study visit:

- The site must attempt to contact the participant and reschedule the missed visit as soon as possible and counsel the participant on the importance of maintaining the assigned visit schedule and ascertain whether or not the participant wishes to and/or should continue in the study.
- Should the participant continue to be unreachable, he/she will be considered to have withdrawn from the study.

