#### 8.2.1. Time Period and Frequency for Collecting AE and SAE Information

Data on adverse events will be collected directly after surgery, and on the 2 postoperative visits.

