#### 9.4.1. General considerations

#### 9.4.2. Primary endpoint(s)

Medication usage; total amount of propofol used (mg/kg/hr) from start to end of anesthesia.

TCI effect site target at start, and each 10 min interval during anesthesia.

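### Section 7.3 counts any discharge before the 24 h assessment as loss to follow-up, which permits avoidable and possibly informative loss of the 24 h cognitive test and the last adverse event review

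*Protocol*

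**What the plan says.** Protocol section 7.3 gives two routes to being lost. The first is early discharge: "A participant will be considered lost to follow-up if he or she is discharged prior to 24 postop assessment". The second is a patient who is "unable to be approached for assessment at local hospital due to transfer from Oslo University Hospital".

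The section then sets out what to do when a visit is missed: "The site must attempt to contact the participant and reschedule the missed visit as soon as possible". Only after that fails does it end participation: "Should the participant continue to be unreachable, he/she will be considered to have withdrawn from the study". It does not say whether these steps apply to a patient already classed as lost by going home.

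What falls due at 24 h:

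- **Cognition.** Section 9.4.3 lists CANTAB with two contrasts: "preoperative function compared with 3hrs after wake-up, and preoperative compared with 24 hrs after wake-up".
- **Safety.** Section 8.2.1 states: "Data on adverse events will be collected directly after surgery, and on the 2 postoperative visits". The schedule in section 1.2 places the two visits at 3 h and 24 h. Section 8.2.2 follows SAEs and AEs of special interest until they resolve, are otherwise explained, or the participant is lost to follow-up.
- **Pain and sedation.** The last assessment in section 1.2 is also at 24 h.

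Section 4.1 says that participants complete CANTAB themselves on an iPad. Section 2.3 promises every patient an interview about the experience of anaesthesia, without fixing its time. Section 9.3 defines the evaluable population as everyone.

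**The concern.** Loss to follow-up normally means that a patient could not be reached. Here it is a label attached to a patient whom staff watch leave, before any attempt at the assessment has failed. A site that follows the definition literally may stop there, and no later analysis can restore data that were never collected.

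The trigger occurs after randomisation and could depend on treatment. The protocol hypothesises lower anaesthetic dosage, faster wake-up and less cognitive dysfunction. If those effects carried through to earlier discharge, the 24 h values would go missing more often in the intervention arm, and the comparison would rest on a selected group.

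There is also a safety side. Awareness with recall is the one unexpected SAE that section 8.2.3 foresees. A patient who goes home before 24 h loses the last review at which it could be reported, and under section 8.2.2 the label can close follow-up of an event already recorded.

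**Working it through.** **1. The protocol's own figure.** Inputs from sections 9.1 and 9.2: difference 3 min, SD 5 min, power 80%, significance level 0.05 (taken as two-sided, which is not stated).

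n per arm = 2 × (1.960 + 0.842)² × 5² / 3² = 43.6, so 44 per arm and 88 in total. The stated 88 is reproduced. The exact t-test gives 44.6, hence 45 per arm. Enrolling 100 leaves 100 − 88 = 12 patients, or 12%, for loss.

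**2. Benchmark for the 24 h comparison.** The protocol sets no target for CANTAB. For an unadjusted two-sample t-test with 50 per arm:

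(1.960 + 0.842) × √(2/50) = 0.56 SD by the normal approximation, and 0.57 SD by the exact t-test.

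**3. What the rule exposes.**

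| Measurement | When recorded | Exposed? |
|---|---|---|
| Propofol use | During anaesthesia | No |
| Wake-up times | At emergence | No |
| CANTAB at 3 h | 3 h | No |
| AE and awareness, earlier reviews | Directly after surgery and at 3 h | No |
| CANTAB at 24 h | 24 h | Yes |
| AE and awareness, last review | 24 h | Yes |

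**4. Size of a possible bias, simple form.** Let p be the share of an arm discharged early and δ the mean 24 h score of leavers minus that of stayers, in SD and equal in both arms. The full-arm mean is the stayers' mean plus pδ, so the retained mean is too low by pδ. The bias in the contrast is −(p_int − p_ctrl) × δ.

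The protocol gives neither p nor δ, so all values here are assumptions:

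| p control | p intervention | δ = 0.5 | δ = 1.0 |
|---|---|---|---|
| 10% | 20% | −0.05 | −0.10 |
| 5% | 25% | −0.10 | −0.20 |

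If p is equal in the two arms, or δ = 0, the bias is zero.

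**5. The same question under a second model.** A latent recovery score decides who leaves before 24 h and has correlation ρ with the 24 h cognitive score. The intervention shifts recovery by s. Again, all inputs are assumptions.

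| s (SD) | p control | p intervention | Bias, ρ = 0.3 | Bias, ρ = 0.6 |
|---|---|---|---|---|
| 0.3 | 6% | 10.5% | −0.02 | −0.05 |
| 0.3 | 12% | 19% | −0.03 | −0.07 |
| 0.3 | 24% | 34% | −0.05 | −0.09 |
| 0.6 | 6% | 17% | −0.05 | −0.11 |
| 0.6 | 12% | 28% | −0.07 | −0.15 |
| 0.6 | 24% | 46% | −0.10 | −0.19 |

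With s = 0 or ρ = 0 the bias is zero apart from simulation error.

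**6. Comparison.** Across both models, when both conditions hold, the bias runs from about 0.02 to 0.20 SD. Against 0.57 SD this is 0.02/0.57 = 4% to 0.20/0.57 = 35% of the detectable difference.

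**The case against.** A reader might infer that the fastest recoverers drop out and that the 24 h comparison is therefore biased against the better arm. The documents do not support that. The hypothesised gain is 3 minutes in wake-up time, and nothing connects it to leaving hospital within a day of elective spinal surgery. Discharge may follow the type of operation or bed logistics. The transfer route in the same sentence has no evident direction. No early-discharge rate is given, and a contrast such as 5% versus 25% is an illustration only. This objection stands, and it makes the bias a conditional possibility.

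A reader might also infer that awareness goes unscreened in early leavers. It does not: events are also collected directly after surgery and at 3 h, and section 2.3 commits to interviewing everyone. Only the last review is lost.

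Further points on the other side:

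- One contrast of one secondary endpoint is exposed, and the evaluable population keeps these patients in every other analysis. This stands.
- Handling of missing 24 h data may belong to the SAP. This also stands, but the point here is a conduct rule that lets data go uncollected.
- The contact-and-rebook step may recover the visit. It may, if it applies, but the section does not say so. That is a conflict of wording to be settled.
- Section 7.1 says of a patient who stops the intervention that "the participant will remain in the study to be evaluated". This concerns a different event and does not settle what happens after discharge.

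**Conclusion.** The defect is in the conduct rule. Section 7.3 makes an observed early discharge a loss in itself, against its own instruction to contact and rebook, and section 8.2.2 lets that label end follow-up of events. The consequence is avoidable loss of the 24 h CANTAB contrast and of the last adverse event and awareness review. That conclusion needs no assumption about bias.

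Bias in the 24 h contrast is possible but not shown. It requires both an effect of the intervention on time to discharge and a relation between discharge and 24 h cognition. If both hold with early leavers performing better and the intervention arm leaving earlier, it would be about 0.02 to 0.20 SD against the intervention, compared with about 0.57 SD detectable. The range rests on assumed discharge rates, an assumed leaver–stayer difference or correlation, and an assumed shift in recovery. Without either condition it is zero under these models.

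The primary propofol result, wake-up times and 3 h cognition are unaffected. The change is worth making because it is cheap and the 24 h data cannot be obtained afterwards.

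**What to change.** Amend section 7.3 as follows:

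1. Delete early discharge as a definition of loss. Treat the patient as remaining in follow-up with a visit still due, and state that the contact-and-rebook step applies.
2. Require that CANTAB, the awareness interview and the AE review be attempted as close to 24 h as possible, off site or by telephone as suits each. If that is not feasible, do them just before departure.
3. Record the actual time since wake-up for each assessment.
4. Report early discharge and assessment time by arm.
5. Account for actual assessment time in the 24 h analysis.

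The fifth item matters. Counting a pre-discharge test at any hour as the 24 h result could confound timing with arm, because an arm that leaves earlier would also be tested sooner after anaesthesia. A sensitivity analysis restricted to a window around 24 h does not cure this, since it excludes the same patients again.

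Section 8.2.2 should be read again after the change, so that going home early does not by itself end follow-up of an event.

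The cost is a short amendment and some organisation of off-site testing and calls. The downside is that some assessments will be off-time or done in a less controlled setting.
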